TITLE	A randomised controlled trial to assess the immunogenicity, safety and reactogenicity of standard dose versus fractional doses of COVID-19 vaccines (Pfizer-BioNTech or Moderna) given as an additional dose after priming with Pfizer-BioNTech or AstraZeneca in healthy adults		
TRIAL DESCRIPTION	This clinical trial will be a single blind*, randomised study to determine the reactogenicity and immunogenicity of booster doses of SARS-CoV-2 vaccines in adults. Both fractional and standard doses will be tested.		
	Primary vaccine	Booster vaccines	
	Pfizer-BioNTech (BNT162b2)	1. Pfizer-BioNTech (BNT162b2 or Comirnaty ®) Standard dose (30µg) n=100	
		2. Pfizer-BioNTech (BNT162b2 or Comirnaty ®) Fractional dose (15µg) n=100	
		3. Moderna (mRNA-1273 or Spikevax ®) Standard Dose (50µg)** n=100	
		4. Moderna (mRNA-1273 or Spikevax ®) Fractional Dose (20µg)** n=100	
	AstraZeneca (ChAdOx1-S, or Vaxzevria ®)	5. Pfizer-BioNTech (BNT162b2 or Comirnaty ®) Standard Dose (30µg) n=100	
		6. Pfizer-BioNTech (BNT162b2 or Comirnaty ®) Fractional Dose (15µg) n=100	
		7. Moderna (mRNA-1273 or Spikevax ®) Standard Dose (50µg)** n=100	
8. Moderna (mRNA-1273 or Spikevax ®) Fractional Dose (20µg)** n=100			

* Subjects and assessors will be blinded to the vaccine allocation for one month (28 days) following administration, and laboratory staff will be blinded to vaccine allocation associated with specimens.
 
**Recent data from UK/USA indicate that reactogenicity is an issue for full dose Moderna (100µg) boosters, hence we are using fractional doses for this vaccine. Currently the recommended standard booster dose is 50µg.
			
OBJECTIVES	
Primary objectives –
 
 To assess and compare the immune response measured as binding antibodies (IgG ELISA) following standard versus fractional doses of Pfizer or Moderna vaccine given as single additional doses in adults 18 years or older in Australia who have been primed through previous vaccination with Pfizer or AstraZeneca vaccines. (Timepoint – 28 days post vaccination) 		

	
 To assess the rate and severity of reactogenicity within one-week post-booster for each group (Timepoint – 7 days post vaccination) 
Secondary objectives - (timepoint –12 months)
 
 To compare the duration of immunity, both humoral and cellular, over 12 months for fractional vs standard booster doses of the vaccines listed. To evaluate the different priming capacities of Pfizer and AstraZeneca vaccines. To evaluate the safety of the booster dose regimens.
OUTCOMES AND OUTCOME MEASURES	
Outcomes:
 
 Reactogenicity will be measured using the accepted standardised method for evaluation of systemic and local side effects following vaccination using a structured questionnaire for seven days post-vaccination. All moderate or severe reactions will be reviewed by study staff. All solicited adverse events (AE) will be collected for 7 days, all unsolicited AE will be collected for 28 days, and all medically attended AE will be collected for 3 months. SAE will be collected throughout the follow up period of 12 months. Adverse events of special interest will be categorised as per CEPI guidelines (1) Antibodies (binding and functional) and cellular immune responses will be measured (see outcome measures for details) 
Reactogenicity
 
 Reactogenicity will be measured by recording the following parameters: 
 Local reaction - pain, tenderness, erythema/redness, induration/swelling Systemic – Nausea/vomiting, headache, fatigue/malaise/myalgia, arthralgia 
Immunology endpoints
 
Binding antibody – These will be evaluated using the commercial Euroimmun S1 IgG ELISA on serum collected at 4 timepoints (baseline, 28 days, 6 months, and 12 months). For all subjects, the 28 days post-vaccination sample will be assayed within four weeks of collection.
 
Functional antibody – All samples will be assayed using the GenScript cPass SARS-CoV-2 Neutralization Antibody detection kit for both WT and Delta variant RBD antigen.
 
Neutralizing antibody - A fraction of samples (20%) will be assessed using a SARS-CoV-2 assay undertaken at the PDI, Melbourne. Testing will be at 4 timepoints for Wuhan strain and 2 Variants of Concern.

	
Cellular immunity - Cellular immunity will be assessed on a 40% subset of samples collected at three timepoints: baseline, 28 days, and 12-months post-vaccination as follows:
 
 • QuantiFERON Human IFN-γ SARS-CoV-2 (Qiagen) will be performed using whole blood. • Assays performed on PBMCs will include IFN-γ Elispot, intracellular cytokine assays (flow cytometry) and multiplex cytokine assays.
TRIAL POPULATION	
Participants will be adults aged 18 years or older who have received two doses of either Pfizer-BioNTech (BNT162b2, or Comirnaty[®]) or AstraZeneca (ChAdOx1-S, or Vaxzevria[®]) 6 to 9 months before entering this study; in line with ATAGI recommendations (2). There will be no upper age limit. Participants will be recruited from staff, their families and acquaintances at the Murdoch Children's Research Institute, the Royal Children's Hospital, the PDI and if necessary, the greater Melbourne area. 100 participants will be recruited per group, and there will therefore be 800 participants in total. Procedures will be implemented to ensure participants of all ages (aged 18 and above) are included and that there is an even age distribution in each group (<50 and \geq50 years).

DESCRIPTION OF SITES ENROLLING PARTICIPANTS	
This will be a single site study with all participants enrolled at RCH

DESCRIPTION OF INTERVENTIONS	
The interventions being studied are as follows:
 
Pfizer-BioNTech (BNT162b2, or Comirnaty[®]) Standard Dose
 
Pfizer-BioNTech (BNT162b2, or Comirnaty[®]) Fractional Dose
 
Moderna (mRNA-1273, or Spikevax[®]) Standard Dose
 
Moderna (mRNA-1273, or Spikevax[®]) Fractional (20μg) Dose

TRIAL DURATION	
The recruitment period will be approximately 4 months. Each participant will have six visits over a follow-up period of 12 months following their immunisation visit.

PARTICIPANT DURATION	
Participant duration will be 12 months, and there will be six visits. The DSMB will review participant safety data monthly. Binding antibody ELISA results (Euroimmun) will be reviewed by the DSMB for all participants who receive a fractional dose, and compared with those who received a full dose. They will review all cases that do not meet the seroresponse definition (p38-39). The DSMB will decide if participants will be offered a further booster dose.

GLOSSARY OF ABBREVIATIONS

ABBREVIATION	TERM
AE	Adverse Event

1. ADMINISTRATIVE INFORMATION

1.1. Trial registration

1.1.1. Trial registry

The trial will be registered on [ClinicalTrials.gov](https://clinicaltrials.gov) prior to trial commencement.

1.3. Expected duration of study

The expected duration of the study is 24 months which includes preparation and reporting. The recruitment period is anticipated to be 3 months and all participants will be followed up for 12 months.

1.5. Stakeholder involvement

The Coalition for Epidemic Preparedness Innovations (CEPI) is a foundation that takes donations from public, private, philanthropic, and civil society organisations to finance independent research projects to develop vaccines against emerging infectious diseases. CEPI is providing funding for this study. CEPI has reviewed this protocol, and they have been involved in the development of the project.

2. INTRODUCTION AND BACKGROUND

2.1. Trial rationale and aim

Additional or booster doses of Covid-19 vaccines are currently being used in a number of countries with minimal data regarding optimal timing, target groups, duration of protection and safety. In addition, there is currently ongoing inequity in vaccine availability in many low- and middle-income countries with vaccine coverage in many countries in Africa at <1% of the eligible population. There are however a number of critical outstanding questions related to the use of booster doses. These include optimal timing, particularly after priming with inactivated vaccines that provide shorter duration of protection, and the potential use of fractional dosage. We have chosen three sites (Australia, Mongolia, and Indonesia) which together will be suitable to answer these questions.

Due to the rapidly developing field much of the data had been presented in various WHO meetings, but is currently unpublished (Appendix 1). Currently the most comprehensive published booster study is the UK-based multi-site CovBoost study (3). This study demonstrated the use of fractional doses of Pfizer vaccine to be very close to equivalent in patients primed with AstraZeneca or Pfizer vaccines. This protocol covers the component to be studied in Australia and will focus on booster regimens relevant to Australia and not previously studied elsewhere in the world.

2.2. Background

It is becoming clear that all Covid-19 vaccines are not equal. While all the EUL listed products effectively prevent severe and fatal Covid-19, prevention of mild or asymptomatic infection is variable, and the duration of protection seems limited and highly variable. As most low- or middle-income countries are struggling to access sufficient Covid-19 vaccines for their population, it may seem inappropriate to be examining options for boosting immunity. We are proceeding with this project for the following reasons:

1. Some countries that have achieved high coverage with inactivated vaccines with little impact on overall disease rates have begun programs of heterologous (e.g., UAE, Mongolia) or homologous (e.g., Chile) boosting, without a strong scientific basis for the schedules chosen. Guidance is needed on how this should be achieved.
2. Countries that have begun vaccination early with support from COVAX have usually started by vaccinating front line health workers (e.g., Indonesia). With minimal vaccination of the general population, health workers have been exposed to large numbers of infected patients and increasing numbers of Covid-19 illness and death among health care workers have led to informal attempts to boost immunity for this group (4).
3. The use of fractional doses as boosters has been shown to produce similar boosting to full doses for two vaccines (Johnson & Johnson (5) and Moderna (6)), and an unpublished study from Thailand (Appendix 1) and recent data from UK (3) have shown a similar effect with half dose Pfizer vaccine. The use of fractional doses for booster doses and potentially primary series could save large volumes of vaccine, potentially freeing up vaccine for communities that currently lack access. Recent guidelines in US and UK recommend the use of half dose (50µg) for Moderna booster doses, while follow-up of earlier studies indicate that a 20µg dose is likely to be adequate as a booster (7-9).

2.3. Risk/Benefit assessment

2.3.1. Known potential risks

This study will provide safety data of the booster regimens being studied and will collect safety data for fractional doses of the booster vaccines.

The safety profiles of the vaccines being tested are well described (see Appendix 2 - Product information sheets).

Possible lower efficacy of fractional booster dose

Participants who receive a fractional dose are at a small risk of not receiving sufficient vaccine to protect against COVID-19 infection.

Risks associated with sample taking

Participants may experience discomfort and/or localised bruising from venepuncture and there is a small risk of fainting. The total volume of blood drawn over a 12-month period will be up to 114mls which is safe in otherwise healthy adults.

Allergic reactions

Allergic reactions may occur to any of the constituents of the booster vaccine. These may range from mild to severe but are usually rare. Patients should be questioned regarding allergic reactions to any vaccines in the past. All participants will have previously received two doses of a Covid-19 vaccine.

Reactogenicity

It is possible that participants might experience more reactogenicity if their booster vaccine is different to the vaccine used in their primary two dose schedule. This is compensated for by the expected superior immunogenicity seen with heterologous boosting schedules.

2.3.2. Known potential benefits

Booster doses of Covid-19 vaccines are available to all adults in Australia and there may be no direct benefits for participants enrolling in this study, apart from the opportunity to learn their antibody response following the booster. In addition, the fractional dose booster may be shown to be equally effective with less reactogenicity. Participants will receive a heterologous boost which may be shown to be superior to a homologous boost. Studies have shown that mRNA boosting potentially offers superior immunogenicity for individuals primed with AstraZeneca (10).

While early reports from Israel and the US confirm the effectiveness of a third dose of Covid-19 vaccine in some heterologous or homologous regimens, there is only limited data on the use of fractional dosage in heterologous regimens. This study will provide data crucial to designing optimal vaccine strategies in Australia and other countries that have used Pfizer-BioNTech (NT162b2, or *Comirnaty*[®]) or AstraZeneca (ChAdOx1-S, or *Vaxzevria*[®]) as primary two dose regimens.

2.3.3. Assessment of potential risks and benefits

Pfizer and Moderna vaccines are currently available to the general population as a booster. The trial component is to examine administration of fractional doses. The risk of fractional doses is the potential for lower effectiveness, while the use of heterologous boosters poses the risks of increased reactogenicity and uncertain effectiveness. These factors are balanced against the potential benefits of heterologous boosting which include preservation of vaccine through the use of fractional doses, and potentially superior immunogenicity and broader protection. It should be noted that the risks and benefits from homologous boosting also remain unclear.

3. TRIAL OBJECTIVES AND OUTCOMES

3.1 Objectives

3.1.1 Primary objective

- The primary objectives of the study are to: -To assess and compare the immune response measured as binding antibodies (IgG ELISA) following standard versus fractional doses of Pfizer or Moderna vaccine given as a single additional dose to adults 18 years or older in Australia who have been primed through previous vaccination with Pfizer or AstraZeneca vaccines. (Timepoint – 28 days post vaccination)
- To assess the rate and severity of reactogenicity within one-week post-booster for each schedule evaluated.

3.1.2 Secondary objectives

The secondary objectives are to: -

- To compare the immunogenicity, both humoral and cellular, over 12 months following fractional and standard booster doses of the vaccines listed.
- To evaluate the different priming capacities of Pfizer and AstraZeneca vaccines
- To evaluate the safety of the booster dose regimens

3.2 Outcomes

3.2.1 Primary outcomes

Immune response

Binding antibody – These will be evaluated using the commercial Euroimmun S1 IgG ELISA on all serum samples collected at 4 timepoints (baseline, 28 days, 6 months, and 12 months). Assays for all subjects will be completed within 4 weeks of sample collection. For subjects who receive a fractional dose, assays on the 28 days post-vaccination sample will be performed within two weeks of collection and reviewed by the DSMB.

Reactogenicity

Reactogenicity will be measured using the accepted standardised method to evaluate systemic and local side effects following vaccination using a structured questionnaire for days post-vaccination as outlined in Table 1 below.

Table 1. Grading system for evaluation of systemic and local side effects following vaccination (11).

Local Reaction to Injectable Product				
	Mild (Grade 1)	Moderate (Grade 2)	Severe (Grade 3)	Potentially Life Threatening (Grade 4)
Pain	Does not interfere with activity	Repeated use of nonnarcotic pain reliever >24 hours or interferes with activity	Any use of narcotic pain reliever or prevents daily activity	ER visit or hospitalization
Tenderness	Mild discomfort to touch	Discomfort with movement	Significant discomfort at rest	ER visit or hospitalization
Erythema/redness ^a	2.5 – 5 cm	5.1 – 10 cm	>10 cm	Necrosis or exfoliative dermatitis
Induration/swelling ^b	2.5 – 5 cm and does not interfere with activity	5.1 – 10 cm or interferes with activity	>10 cm or prevents daily activity	Necrosis

^a The measurement should be recorded as a continuous variable in addition to grading the measured local reaction at the greatest single diameter.
 
^b Induration/swelling should be evaluated and graded using the functional scale as well as the actual measurement.
				
Systemic (General)				
	Mild (Grade 1)	Moderate (Grade 2)	Severe (Grade 3)	Potentially Life Threatening (Grade 4)
Fever (°C) Oral or axillary temperature	38.0 – 38.4	38.5 – 38.9	39.0 – 40	>40
Nausea/vomiting	No interference with activity or 1 – 2 episodes /24 hours	Some interference with activity or >2 episodes/24 hours	Prevents daily activity, or requires outpatient IV hydration	ER visit or hospitalization for hypotensive shock
Headache	No interference with activity	Repeated use of nonnarcotic pain reliever >24 hours or some	Significant; any use of narcotic pain reliever or prevents daily activity	ER visit or hospitalization

		interference with activity		
Fatigue/Malaise	No interference with activity	Some interference with activity	Significant; prevents daily activity	ER visit or hospitalization
Myalgia (muscle pain)	No interference with activity	Some interference with activity	Significant; prevents daily activity	ER visit or hospitalization
Arthralgia (joint stiffness)	No interference with activity	Some interference with activity	Significant; prevents daily activity	ER visit or hospitalization
In addition, appearance of the following potential signs of myocarditis/pericarditis will prompt referral for cardiology evaluation: Chest pain, dyspnoea, painful breathing, palpitations, or syncope.				

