7.2 Description of procedures

7.2.1 Visit 1 (Day 0)

Informed consent must be signed by both participant and study doctor or nurse.

Participant eligibility must be confirmed prior to randomisation and on the same date as administration of the investigational product.

Eligibility must be confirmed by a study doctor or study nurse. Randomisation must be completed by the unblinded vaccinator who will document the participant's randomisation number on the enrolment log.

Study staff will administer a Visit 1 questionnaire documenting demographic information, height and weight, dates and type of primary COVID-19 vaccine, any comorbidities and concomitant medication.

The following vital signs will be recorded by a study doctor or study nurse prior to vaccination: temperature, pulse rate, respiratory rate, and blood pressure.

Prior to vaccination, for all participants, 5mL of blood will be collected and processed according to the SOP. CMI participants will have an additional 25ml collected and processed for Quantiferon analysis and PBMC separation and storage.

Following randomisation, the unblinded vaccinator will administer the applicable vaccine to the participant.

The following vital signs will be recorded by a study doctor or study nurse 15 minutes following vaccination: temperature, pulse rate, respiratory rate, and blood pressure.

Study staff will provide participant with reactogenicity diary card and instruct the participant on how to complete the diary card up to and including 7 days following vaccination.

Study staff will provide the participant with a thermometer and ruler and detailed instructions on how to use these for measuring temperature and potential erythema and induration. Study staff will provide the participant with a schedule of visit appointments and instruct the participant on how to contact the study staff in case of any SAE or symptoms suggestive of COVID-19.

Study staff will keep the participant under observation for minimum 15 minutes and document any immediate adverse events.

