7.2.3 Visit 4 (Day 28)

An in-person visit will be conducted 28 days following vaccination. All Unsolicited Adverse Events will be documented. Study staff will also document any new information regarding solicited adverse events with onset up to 7 days following vaccination, such as resolution. The participant will be informed which vaccine they received based on entry into the CRF by an unblinded staff member.

For all participants, 5mL of blood will be collected in an SST tube. For participants in the CMI subset, 3mL of blood for Quantiferon test will be collected in a heparinised tube, and 20mL of blood for PBMC will be collected in a heparinised tube. Blood samples will be kept at room temperature and transferred to the laboratory within 3 hours of collection.

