11.3 Methods of analysis

Reactogenicity following immunisations will be presented as the number and percentage of participants self-reporting local reactions (pain; tenderness, redness; swelling at or near the injection site) and systemic reactions (fever, nausea/vomiting, headache, fatigue/malaise, myalgia), and the severity of

these reactions (mild, moderate, severe, life-threatening or fatal). Reactogenicity data will be presented separately by group and time point.

For immunogenicity, antibody levels will be presented as geometric mean titres (GMT) with 95% confidence intervals. Changes from baseline will be expressed as geometric mean fold ratios (GMFR), calculated as the ratio of the post-booster GMT to the baseline GMT. Seroresponse will be defined as a ≥ 4 -fold rise in post-booster antibody levels compared to baseline (or ≥ 2 -fold rise if the baseline (pre-booster) antibody level was ≥ 200 BAU/ml). To assess the non-inferiority of the fractional dose compared with the standard dose, comparisons will be based on the difference in percentage of participants with seroresponse. Using a non-inferiority margin of -10% (fractional-dose minus standard dose), non-inferiority will be declared if the lower limit of the 95% confidence interval around the difference in percentages is greater than -10%, where confidence intervals are calculated using Score-based methods (14)

Analyses will be performed using Stata software (15). Detailed methodology will be outlined in a separate Statistical Analysis Plan.

Primary outcome (All samples at all timepoints)

The binding IgG data using the Euroimmun S1 IgG ELISA kits will be reported as relative units/ml (RU/ml) as per manufacturer's instructions. A result of < 8 RU/ml: negative (IgG Antibodies for SARS-CoV-2 are not detected), ≥ 8 to < 11 RU/ml: borderline (IgG antibodies is indeterminate/equivocal with this sample), ≥ 11 RU/ml: positive (IgG antibodies for SARS-CoV-2 are detected). Conversion to binding antibody units (BAU/ml) will also be done using the WHO reference serum from NIBSC, UK. Data will be presented as geometric mean titres and 95% confidence intervals.

Analysis comparing fractional and standard dose groups will be based on seroresponse rate (SRR) at 28 days post study vaccine, defined as:

- ≥ 4 -fold rise in GMCs at 28 days post study vaccine from baseline among subjects with no pre-dose (< 200 BAU/ml) detectable titres

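### Section 3.2.1, read literally, has the baseline serum assayed before the day-28 serum is available, and no rule puts the pair in one run; avoidable between-run error can enter the fold rise that defines seroresponse

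*Combined protocol and SAP*

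**What the plan says.** Section 3.2.1 says the Euroimmun S1 IgG ELISA will be run "on all serum samples collected at 4 timepoints (baseline, 28 days, 6 months, and 12 months"). The next sentence sets the deadline: "Assays for all subjects will be completed within 4 weeks of sample collection". For fractional-dose recipients it adds that "assays on the 28 days post-vaccination sample will be performed within two weeks of collection and reviewed by the DSMB".

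The synopsis (immunology endpoints) words the limit differently: "For all subjects, the 28 days post-vaccination sample will be assayed within four weeks of collection". It sets no deadline for baseline serum.

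On timing of the draws, section 7.2.1 (Visit 1, day 0) says "Prior to vaccination, for all participants, 5mL of blood will be collected and processed according to the SOP". Section 7.2.3 says "An in-person visit will be conducted 28 days following vaccination", and the schedule in section 7.1 gives that visit a window of plus 7 days with no minus side.

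On the endpoint, section 11.3 says "Seroresponse will be defined as a ≥ 4 -fold rise in post-booster antibody levels compared to baseline", with a 2-fold rise sufficient when baseline is at least 200 BAU/ml. Section 11.3 also plans conversion to BAU/ml against the WHO reference serum.

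**The concern.** A fold rise is a ratio of two assay results from one person. If both sera are on one plate, error common to that plate largely cancels. If they are in different runs, the ratio carries the error of both, and people near the 4-fold or 2-fold cut-off can be classified wrongly for reasons unrelated to dose.

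Two uses of the endpoint are affected. The non-inferiority comparison of fractional with standard dose rests on the seroresponse percentages. The DSMB also reviews every participant who does not meet the definition (synopsis, participant duration) and assesses responses individually as well as by group (section 11.4).

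A laboratory following section 3.2.1 would separate the pair; one following the synopsis need not.

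**Working it through.** **Dates**
- Baseline is drawn on day 0. Under section 3.2.1 it is due by 0 + 28 = day 28.
- The Visit 4 serum is drawn between day 28 and 28 + 7 = day 35.
- The baseline deadline therefore falls 0 to 7 days before the second serum exists. One run meeting section 3.2.1 is possible only if Visit 4 falls exactly on day 28 and the plate is run that day.
- Under the synopsis there is no conflict. Baseline can be held and run with the day-28 serum within 28 days of the day-28 draw (14 days in the fractional arms under section 3.2.1).

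**Reproducing the planned power**

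Inputs from sections 11.1 and 11.3: n = 100 per group, margin 10 points, lower limit of a two-sided 95% interval.

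Power = Φ[(0.10 − (p_s − p_f))/SE − 1.96], with SE = √[p_s(1 − p_s)/100 + p_f(1 − p_f)/100], where s is standard and f fractional.
- 95% v 95%: SE = 0.0308; Φ(3.244 − 1.960) = 0.90. The plan states 90%.
- 95% v 93%: SE = 0.0336; Φ(2.384 − 1.960) = 0.66. The plan states 66%.

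Both reproduce with this normal approximation. I use it below to show the change, although the planned analysis uses a score-based interval.

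**Adding between-run error**

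Assumptions not in the documents:
- log-normal fold rise with ln SD s of 0.7 to 1.0 and a single cut-off;
- seroresponse p (95% or 93%) when there is no between-run error;
- two runs with independent error and equal CV;
- errors independent between participants.

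Added ln SD: e = √[2 ln(1 + CV²)]. Observed seroresponse = Φ[z_p × s/√(s² + e²)].

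Example, CV 20% and s = 0.7: e = √(2 ln 1.04) = 0.280; s/√(s² + e²) = 0.928; seroresponse = Φ(1.645 × 0.928) = 93.7%; SE = 0.0345; power = Φ(0.10/0.0345 − 1.96) = 83%.

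| Per-run CV | Observed seroresponse (95% without error) | Power, 95% v 95% (planned 90%) | Power, 95% v 93% (planned 66%) |
|---|---|---|---|
| 10% | 94.7–94.8% | 88–89% | 63–65% |
| 20% | 93.7–94.3% | 83–86% | 56–61% |
| 30% | 92.1–93.6% | 75–82% | 47–55% |

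Ranges run from s = 0.7 to s = 1.0.

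**Direction of the effect** (CV 30%, s = 0.7)
- 95% v 93% becomes 92.1% v 89.8%. The gap widens from 2.0 to 2.4 points.
- At the margin, 95% v 85% becomes 92.1% v 81.4%. The gap widens from 10.0 to 10.8 points, and the chance of falsely declaring non-inferiority falls from 2.5% to 1.7%.
- Over CV 10% to 30% and s = 0.7 to 1.0, that chance is 1.7% to 2.4%, always below 2.5%.

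**The case against.** **Separation is not certain.** The synopsis allows baseline serum to be held, and a completion deadline does not forbid re-assaying stored serum. Serum processing follows an SOP that is not among the documents and may fix the plate layout. This stands: between-run error is something that can enter the fold rise, not something that must. The two places still conflict, and the stricter one is the section that defines the primary outcome.

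**Calibration helps.** Conversion to BAU/ml with the WHO reference serum should remove part of any between-run shift. This stands in part, because a common reference does not remove plate-level error. The CVs in the table are best read as what remains after calibration.

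**A reader might infer that noise makes the arms look alike and so favours non-inferiority.** The calculation does not support this. At the plan's response rates, random run error widens the gap and makes a false claim slightly less likely.

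**A reader might infer large errors from a systematic shift.** In the same model, if every day-28 run read 20% low relative to baseline, 95% seroresponse would become 90.8–92.2%. That needs one uncorrected shift, in one direction, across all plates over a recruitment period of three to four months, and nothing in the documents shows one. The baseline timing rule is also the same in all arms, whereas the 10-point margin applies to the difference between arms.

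**A reader might infer a bias between arms from the two-week limit for fractional-dose sera.** That is a maximum time and does not by itself put the arms in different runs. It is, however, a further reason to apply the pairing rule to all arms.

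**Conclusion.** The point holds in a limited form. Section 3.2.1 and the synopsis conflict on when baseline serum is due. The literal reading of section 3.2.1 separates each pair in all but a same-day case, and no paired-run or re-assay rule appears in the documents.

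The consequence is lost power and some misclassified individuals in the DSMB's case review. The loss is 1 to 2 points from the planned 90% at a per-run CV of 10%, 4 to 7 points at 20%, and 8 to 15 points at 30%. These figures are illustrative. They rest on assumed CVs and fold-rise SDs, and they ignore two features: participants on one plate share run error, and error in the baseline result can change which cut-off applies.

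The case for acting is that the loss is avoidable at almost no cost, not that the primary conclusion would be biased.

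**What to change.** Reconcile section 3.2.1 with the synopsis, and replace the general deadline in section 3.2.1 with wording such as:

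> *Baseline serum will be stored and assayed on the same plate as the same participant's day-28 serum, in all arms, within the limit counted from the day-28 draw. If baseline serum is assayed earlier, it will be re-assayed with the day-28 serum and the paired result used for seroresponse. The 6- and 12-month sera will be assayed within 4 weeks of collection.*

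State the day-28 limit explicitly for every arm, so that removing the present sentence leaves no sample without one. Carry the pairing rule into the laboratory SOP.

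**Cost.** If baseline serum is stored, the number of assays is unchanged; any baseline serum already run needs one repeat. Under a four-week limit, baseline results are due by day 56 to 63 instead of day 28. Under the two-week limit they are due by day 42 to 49. No planned decision needs them sooner: eligibility (section 4.4) uses no titre, and the DSMB's first antibody review is of one-month data. The practical burden is that baseline sera from the fractional arms, 4 × 100 = 400 participants, must be run inside the two-week window with their day-28 sera.
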